12.1.1 Study Treatment

Refer to Section 6 and Section 12.4 for information on AZD0466; further details are provided in the IB.

12.1.1.1 Non-investigational Product –Voriconazole

Voriconazole is a triazole antifungal medication used to treat serious fungal infections (including invasive candidiasis, invasive aspergillosis, and emerging fungal infections) that occur commonly in patients who are immunocompromised. Voriconazole and other azole antifungal agents are substrates and inhibitors of CYP3A isoforms, and are commonly used for prophylaxis and treatment of fungal infections in patients with acute leukaemia.

The safety profile of voriconazole in adults is based on an integrated safety database of more than 2000 subjects (including 1603 adult patients in therapeutic trials) and an additional 270 adults in prophylaxis trials. This represents a heterogeneous population, containing patients with haematological malignancies, patients with HIV infection with oesophageal candidiasis and refractory fungal infections, non-neutropenic patients with candidaemia or aspergillosis, and healthy volunteers. The most commonly reported adverse reactions during treatment with voriconazole were visual impairment, pyrexia, rash, vomiting, nausea, diarrhoea, headache, peripheral oedema, LFT abnormal, respiratory distress, and abdominal pain. The severity of the adverse reactions was generally mild to moderate. No clinically significant differences were seen when the safety data were analysed by age, race, or gender ([Voriconazole Prescribing Information](#)).

12.1.2 Nonclinical Information and Correlative Studies

Preclinical studies of AZD4320 indicate that CYP3A4 may have a major role in the metabolic clearance of AZD4320, the active moiety of AZD0466.

12.1.3 Rationale for Module 2

Drug interactions with CYP3A4 can lead to its inhibition, which can increase drug effect, or to its induction, which can decrease the drug effect. Medicines that are potent CYP3A4 inhibitors include azole antifungals such as voriconazole or itraconazole. Preclinical studies of AZD0466 have identified CYP3A4 as likely to have a significant role in the metabolic clearance of AZD4320.

Drugs that act as inducers or inhibitors of CYP3A4 may affect circulating levels of the active moiety AZD4320 and could alter the efficacy or tolerability of study treatment. Use of voriconazole and other azole antifungal agents is prohibited in Module 1 of this study as it is not known whether a DDI exists between AZD0466 and azole antifungal agents. This prohibition restricts the therapeutic options for management of fungal infections in the population of patients enrolled in Module 1.

Module 2 will investigate the safety, PK, and tolerability of AZD0466 when co-administered with voriconazole, a strong inhibitor of CYP3A4. The investigation of a potential DDI between AZD0466 and voriconazole will inform the continuation or removal of restrictions on use of azole antifungal agents in ongoing and future study modules.

12.1.4 Justification for Module 2 Dose

Module 2 will be initiated by the SRC (Appendix [A 5](#)) after a tolerated dose of AZD0466 has been determined in Module 1.

12.1.5 Module 2 Study Design

Module 2, a Phase I DDI study of AZD0466 and the azole antifungal agent voriconazole, will be conducted in patients with AML or ALL to determine the effect of voriconazole on the PK of AZD0466. This module will be conducted in selected sites in parallel with Module 1.

During periods of parallel enrolment, patient entry into Module 1 will be prioritised at sites conducting both Module 1 and Module 2 of this protocol.

The Module 2 Cycle 1 schedule includes Periods 1, 2 and 3. Period 1 involves dose ramp-up in from a starting dose of AZD0466 on Day 1, with subsequent titration to the intermediate dose on Day 4, and to the target dose on Day 8. In Period 2, patients will receive a loading dose of oral voriconazole on Day 11 followed by maintenance dosing on Days 12, 13, and 14, as specified in the prescribing information for voriconazole ([Voriconazole Prescribing Information](#)). In Period 3, the dose of AZD0466 administered on Day 15 in combination with voriconazole (at maintenance dose) will be a dose reduction of the target dose (ie, the Day 1 equivalent dose), to mitigate against a potential increase in exposure to the active moiety AZD4320 if a DDI exists between AZD0466 and voriconazole, with a return to the full target dose at the next AZD0466 administration day.

A visual representation of the DDI component of Module 2 (Cycle 1) is shown in [Figure 4](#).

Figure 4 Schema for Cycle 1 of Module 2

AZD0466 IV	Period 1: D1-D10			Period 2: D11-D14		Period 3: D16-D21	
	AZD0466 ramp-up			Voriconazole only		AZD0466+ voriconazole	
AZD0466 IV	D1	D4	D8	D11	D12-D14	D15	D16-D19
	RU1	RU2	TD*			D1 dose**	
Voriconazole PO				400mg BID	200mg BID	200mg BID***	

* The target dose (TD) of AZD0466 is the highest dose level determined as tolerated by the SRC in Part A of Module 1 at the point of first patient enrolment in Module 2.

**After reaching AZD0466 TD at D8 there will be a dose reduction on D15 to the D1 equivalent dose, with a return to full TD at the next AZD0466 administration day.

*** Voriconazole administration will be discontinued on Day 19 after collection of the last PK blood sample. BID, twice a day; D, Day; IV, intravenous; PK, pharmacokinetic; PO, by mouth; RU1: first ramp-up dose; RU2: second ramp-up dose; SRC, Safety Review Committee; TD, target dose.

A minimum of 10 and up to 14 patients overall will be enrolled at selected sites to investigate the potential DDI between AZD0466 and voriconazole.

The DDI part of Module 2 (Cycle 1) will be performed in 3 periods over 21 days (Table 25), as follows:

- Period 1 (Days 1-10): AZD0466 infusion on Days 1, 4, and 8
- Period 2 (Days 11-14): Voriconazole administration bid
- Period 3 (Days 15-21): AZD0466 infusion on Day 15 (at the Day 1 equivalent dose) in combination with voriconazole bid on Days 15-19.

Module 2 Cycle 1 (DDI Part) will utilise a target dose of AZD0466 that has been declared tolerable in the dose escalation Part A of Module 1 (Table 22). After reaching the target dose at Day 8, there will be a dose reduction at Day 15 to the Day 1 equivalent dose, and thereafter there will be a return to the full target dose.

In Module 2 Cycle 2 (after the DDI part), patients may receive AZD0466 as monotherapy at a higher target dose, if a new higher AZD0466 dose level was declared tolerable in Module 1. This dose increase may be implemented without a dose ramp-up. This will allow patients to continue to receive study treatment at a tolerated dose within the predicted efficacious dose range in humans (see Section 11.1.3.1).

Patients who do not wish to continue receiving AZD0466 will undertake the follow-up assessments detailed in Section 7.

Table 22 Module 2 AZD0466 Dose Guidance

AZD0466 Dose*				
Module 2, Cycle 1				Module 2, Cycle 2 and Beyond
D1 RU	D4 RU	D8 TD	D15 (dose equivalent to D1 dose)	D1, D8, D15, D22
75 mg	150 mg	300 mg ^a	75 mg	300 mg weekly ^b
150 mg	300 mg	600 mg ^a	150 mg	600 mg weekly ^b
300 mg	600 mg	1200 mg ^a	300 mg	1200 mg weekly ^b
600 mg	1200 mg	2400 mg ^a	600 mg	2400 mg weekly ^b
1200 mg	2400 mg	3600 mg ^a	1200 mg	3600 mg weekly ^b
2400 mg	3600 mg	5400 mg ^a	2400 mg	5400 mg weekly ^b

^a Module 2 Cycle 1 will utilise a target dose of AZD0466 that has been declared tolerable in the dose escalation Part A of Module 1.

^b Patients may receive AZD0466 after Cycle 1 of Module 2 at a higher target dose, without dose ramp up required, if a subsequent AZD0466 dose level has been declared tolerable in Part A of Module 1.

* Doses displayed are for guidance only. Definitive target and ramp-up doses will be decided by the SRC in Module 1 and communicated accordingly.

D, day; RU, ramp up; SRC, Safety Review Committee; TD, target dose.

In Cycle 1, patients will be admitted as inpatients for 36 hours on Days 1-2, 4-5, 8-9, and overnight on Day 15. Additional inpatient admission days will be at the Investigator's discretion. During Period 2, voriconazole administration will occur on an outpatient basis.

Overnight stays will be required during Cycle 2 Day 1 and Day 8. Thereafter, dosing as an inpatient will be as per Investigator discretion, based on prior tolerability and risk of TLS.

The SoA for the DDI part (Cycle 1) of Module 2, including PK sampling times, is provided in Section 12.5.1.

The SRC may assess safety data from Module 2 that could affect the conduct of Module 1.

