6.6 Dose Modification and Toxicity Management

AZD0466 may be withheld and the dose reduced due to haematological or non-haematological toxicities. In general, no AZD0466 dose modification is required if a patient experiences a Grade 1 or Grade 2 AE. However, AZD0466 should be modified or discontinued when the AEs described in this section are observed whether during ramp-up or once target dose is reached. Modifications based on cardiac AEs are described in Section 6.6.5.

Acceptable dose modifications shown in Table 4 are applicable during ramp-up and once target dose is reached. A maximum of 3 dose modifications are acceptable, except for CTCAE Grade 3 or 4 haemorrhage and any intracranial haemorrhage or haematoma, of which only one event is allowed. Also see Table 5, Table 6, Table 7, and Table 8.

Table 4 Dose Reduction Modifications

Cohort level	AZD0466 dose	Dose reductions		
		1 lower dose	2 lower doses	3 lower doses
DL-1	37.5 mg	--	--	--
	75 mg	37.5 mg	--	--
	150 mg	75 mg	37.5 mg	--
DL1	75 mg	37.5 mg	--	--
	150 mg	75 mg	37.5 mg	--
	300 mg	150 mg	75 mg	37.5 mg
DL2	150 mg	75 mg	37.5 mg	--
	300 mg	150 mg	75 mg	37.5 mg
	600mg	300 mg	150 mg	75 mg
DL3	300 mg	150 mg	75 mg	37.5 mg
	600 mg	300 mg	150 mg	75 mg
	1200 mg	600 mg	300 mg	150 mg
DL4	600 mg	300 mg	150 mg	75 mg
	1200 mg	600 mg	300 mg	150 mg
	2400 mg	1200 mg	600 mg	300 mg
DL5 ^a	1200 mg	600 mg	300 mg	150 mg
	2400 mg	1200 mg	600 mg	300 mg
	3600 mg	2400 mg	1200 mg	600 mg
DL6 ^a	2400 mg	1200 mg	600 mg	300 mg
	3600 mg	2400 mg	1200 mg	600 mg
	5400 mg	3600 mg	2400 mg	1200 mg
DL6 – alternative ramp-up ^b	1400 mg	600 mg	300 mg	150 mg
	2800 mg	1200 mg	600 mg	300 mg
	5400 mg	3600 mg	2400 mg	1200 mg

^a AZD0466 doses shown are illustrative. Actual doses will not exceed a 2-fold increase of a dose declared tolerable by the SRC, or the maximum feasible dose as specified in Section 11.4.7.5.

^b SRC to determine ramp-up as well as target dose.

DL, dose level; SRC, Safety Review Committee

While on study, patients diagnosed with COVID-19 and are thought to be receiving clinical benefit as deemed by the investigator may continue to receive AZD0466; however, must pause treatment if they meet pause or discontinuation criteria for dose modifications based on haematological parameters (Section 6.6.1, neutropenia), or CTCAE Grade 2 or higher non-haematological toxicities (Section 6.6.3), which would include pneumonia or other infectious complications.

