11.1.3.3 Dose Escalation, De-escalation, and Stopping Decision Rules

A SRC (Appendix A 5) will be responsible for making recommendations for dose-escalation or de-escalation after each dose level, including decisions on opening cohorts for backfill, in accordance with the SRC charter. The intra-patient dose ramp-up and/or dose schedule for each cohort may be modified based on safety, PK, and PD findings of a previous dose level. The SRC will also assess all evaluable patients to establish the recommended Phase II dose (RP2D) and determine if the study should progress to Part B.

A recommended dose level for each subsequent cohort of patients will be made by the SRC, guided by pre-defined decision rules. The decision rules are based on a mTPI-2 design (Guo et al 2017) with a 30% ($\pm 5\%$) target DLT rate for maximum tolerated dose (MTD). Depending on the number of patients treated at a dose level, and the number of DLTs observed in those patients, the possible decisions will be: to escalate, stay at current dose, de-escalate, or de-escalate and do not use current dose again due to unacceptable toxicity. Decision rules based on mTPI-2 for dose escalation are shown in [Table 10](#).

The decisions on the adequacy of the dose escalation portion of the design were based on outcomes from an internal AZ simulation package which calculates estimates of the likelihood of selecting the true MTD under a range of different scenarios. Operating characteristics are

presented in Table 11.

Table 10 Decision Rules Based on mTPI-2 for Dose Escalation

Number of DLTs	Number of Patients Treated at Current Dose Level											
	n = 1	n = 2	n = 3	n = 4	n = 5	n = 6	n = 7	n = 8	n = 9	n = 10	n = 11	n = 12
0	S ^a	S ^a	E	E	E	E	E	E	E	E	E	E
1	S ^b	S ^b	S	S	E	E	E	E	E	E	E	E
2		DNT	D	D	D	S	S	E	E	E	E	E
3			DNT	DNT	D	D	D	S	S	S	S	E
4				DNT	DNT	DNT	D	D	D	D	D	D
5					DNT	DNT	DNT	DNT	DNT	D	D	D
6						DNT	DNT	DNT	DNT	DNT	DNT	D
7							DNT	DNT	DNT	DNT	DNT	DNT

^a Adapted from [Guo et al 2017](#) from E to S as a minimum of 3 evaluable patients are needed to make a dose escalation decision.

^b Adapted from [Guo et al 2017](#) from D to S as a minimum of 3 evaluable patients are needed to make a dose de-escalation decision.

D, de-escalation to the next lower dose level; DLT, dose -limiting toxicity; DNT, dose not tolerated; E, escalation to the next higher dose level; mTPI-2, modified toxicity probability interval; S, stay at the current dose level.

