Patients will be admitted to hospital and receive a starting ramp-up dose of AZD0466 on Day 1, with subsequent intra-patient ramp-up to an intermediate dose on Day 4, and to the target dose on Day 8. The Day 1 and Day 4 ramp-up doses will be equivalent to those used for that target dose in Module 1.
- Period 2: Voriconazole administration
Patients will receive voriconazole 400 mg twice daily (BID) on Day 11 and voriconazole 200 mg BID on Day 12-14.
- Period 3: AZD0466 in combination with voriconazole
Patients will be admitted to hospital and receive AZD0466 on Day 15 at a reduced dose (ie, dose equivalent to the Day 1 dose) and voriconazole 200 mg BID will continue from Day 15 until Day 19. Voriconazole administration on Day 19 will not continue beyond the time of last PK sample collection.

Voriconazole tablets should be taken at least one hour before or one hour after a meal, on each of the voriconazole dosing days.

Patients who continue to receive AZD0466 in Cycle 2 may receive AZD0466 at a higher target dose if a new higher dose level was declared tolerable in the dose escalation part of Module 1. Cycle 2 and subsequent cycles are 28 days in duration in which AZD0466 is administered once weekly on Days 1, 8, 15, and 22 of each cycle. All patients will be treated until progressive disease, unacceptable toxicity or withdrawal of consent.

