12.7.2 Sample Size Determination

The number of subjects is based on the desire to gain adequate information on the effect of voriconazole on the exposure of AZD4320, while exposing as few subjects as possible to study procedures.

Interpretation of the results will be based on the estimated effect (geometric mean ratio; GMR) and associated 90% CI.

Assuming an intrapatient CV of 30%, 10 PK evaluable participants are expected to give a relative precision of 2.0 (ratio between the upper and lower limits of the 90% CI) with a probability greater than 80%. This corresponds to a 90% CI of 2.83 to 5.66 if the observed ratio is 4.00 (based on in-vitro data). Up to 14 patients will be enrolled to ensure that at least 10 evaluable patients complete the study.

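### No protocol text limits the Module 2 Day 15 dose to about a quarter of target; the Table 22 guidance cuts it 4-fold up to 2400 mg but only 3-fold at 3600 mg and 2.25-fold at 5400 mg

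*Protocol*

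**What the plan says.** Protocol 12.1.5 sets the AZD0466 dose given with voriconazole by reference to Day 1. On Day 15 it "will be a dose reduction of the target dose (ie, the Day 1 equivalent dose), to mitigate against a potential increase in exposure". The Figure 4 footnote defines the Module 2 target as the "highest dose level determined as tolerated by the SRC in Part A of Module 1 at the point of first patient enrolment".

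Table 22 lists guidance doses. For targets of 300, 600, 1200, 2400, 3600 and 5400 mg, the Day 15 doses are 75, 150, 300, 600, 1200 and 2400 mg. The footnote leaves the decision to the Safety Review Committee (SRC): "Doses displayed are for guidance only. Definitive target and ramp-up doses will be decided by the SRC in Module 1 and communicated accordingly". Section 12.4.1 takes the ramp-up from monotherapy: "The Day 1 and Day 4 ramp-up doses will be equivalent to those used for that target dose in Module 1". Section 11.1.3.3 lets the SRC change ramp-ups, since the "dose schedule for each cohort may be modified based on safety, PK, and PD findings of a previous dose level". Table 4 in 6.6 also lists an alternative dose level 6 ramp-up of 1400/2800/5400 mg, with the note "SRC to determine ramp-up as well as target dose". Table 22 does not include it.

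The protocol's only numerical interaction ratio is in 12.7.2, where the confidence interval is worked out "if the observed ratio is 4.00 (based on in-vitro data").

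SAP 11.1 says that the combination dose is one quarter of target. Elsewhere the same section gives the Day 1 equivalent rule.

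**The concern.** Tying Day 15 to Day 1 keeps the interaction comparison valid, because both infusions are at the same dose. It does not by itself fix the safety margin. The margin depends on how far Day 1 lies below target, and that was chosen for monotherapy ramp-up. Where doses double from Day 1 to Day 4 to Day 8, Day 1 is a quarter of target and a 4-fold interaction is offset. At dose levels 5 and 6 the guidance ramp-up is flatter, so the same rule gives a smaller cut.

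Because the target is the highest dose tolerated when Module 2 opens, exposure above target is exposure above any level cleared at that point. The amendment rationale at the front of the protocol makes the same observation: it warns that more than a quarter of target on Day 15 may leave too little margin, especially at dose level 6. That is supporting context, not a conflict with the current text.

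**Working it through.** **Inputs.** Target and Day 15 doses: Table 22. Alternative dose level 6 ramp-up: Table 4. Interaction ratio R = 4.00, CV 30%, n = 10: section 12.7.2. Values R = 2 and R = 3 are assumptions added to show the range.

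**The plan's own figure.** An upper-to-lower limit ratio of 2.0 around 4.00 gives 4.00/√2 = 2.83 and 4.00 × √2 = 5.66, as stated. With log-scale within-patient SD √ln(1 + 0.30²), paired-difference SD √2 times that, and t on 9 degrees of freedom, the probability of a limit ratio of 2.0 or less is 97.2%. The claim of more than 80% holds. The precision statement is not in question.

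**Formulas**, assuming exposure proportional to dose:
- fraction f = Day 15 dose / target dose
- fold cut = 1/f, which is also the ratio above which Day 15 exposure exceeds target exposure
- Day 15 exposure relative to target = R × f

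| Target (mg) | Day 15 (mg) | f | Fold cut | R = 2 | R = 3 | R = 4.00 |
|---|---|---|---|---|---|---|
| 300 to 2400 | 75 to 600 | 25.0% | 4.00 | 0.50 | 0.75 | 1.00 |
| 3600 | 1200 | 33.3% | 3.00 | 0.67 | 1.00 | 1.33 |
| 5400 | 2400 | 44.4% | 2.25 | 0.89 | 1.33 | 1.78 |
| 5400 (Table 4 alternative) | 1400 | 25.9% | 3.86 | 0.52 | 0.78 | 1.04 |

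For example, 4.00 × 1200/3600 = 1.33, 4.00 × 2400/5400 = 1.78 and 4.00 × 1400/5400 = 1.04.

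**Last ramp-up step (Day 4 to Day 8).** Guidance: 3600/2400 = 1.50 and 5400/3600 = 1.50. Rows up to 2400 mg: 2.00. Table 4 alternative: 5400/2800 = 1.93. A quarter-based ramp-up of 900/1800/3600 or 1350/2700/5400 mg: 3600/1800 = 2.00 and 5400/2700 = 2.00.

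**The case against.** The case on the other side is substantial.

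- The protocol says mitigate, and a 3-fold or 2.25-fold cut does mitigate. At a ratio of 2, even the 5400 mg row stays below target (0.89). This stands.
- In 12.7.2 the 4.00 illustrates interval width. The section does not say whether it refers to AUC or Cmax, or to total or released AZD4320. The multiples therefore hold only for the measure to which 4.00 applies. This stands.
- Section 11.1.3.1 allows escalation of up to 2-fold over a tolerated dose, and 1.33 and 1.78 lie inside that. This stands at a ratio of 4.00, and up to 2 × 3.00 = 6.00 and 2 × 2.25 = 4.50 for the two rows. But that limit governs SRC-reviewed escalation, not an unplanned rise in exposure in an interaction study.
- Table 22 is guidance. If the SRC adopted the 1400 mg start in Module 1, 12.4.1 would carry it into Module 2. True, but no criterion directs the SRC to protect the Day 15 margin.
- Day 15 is supervised. Sections 12.1.5 and 12.4.1 both plan admission. Section 12.6.2.9.12 words the overnight stay as a recommendation, so the wording is uneven, but admission is planned. Vital signs run to 96 hours, ECGs to 72 hours, and liver tests must be reviewed before the infusion.

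A reader might infer that patients were overexposed, or that the higher exposures are unsafe. The documents show neither. They do not say whether any Module 2 patient received dose level 5 or 6, and they give no toxicity threshold that these multiples cross. The maximum feasible dose in 11.4.7.5 is a manufacturing limit and is no benchmark for tolerability. A reader might also infer that SAP 11.1 imposes a quarter-of-target cap. It does not: a SAP does not govern dosing, and the same section also states the Day 1 rule.

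**Conclusion.** The gap is real but conditional. No current protocol text limits the Day 15 dose to about a quarter of target, and the guidance margin falls from 4-fold to 3-fold and 2.25-fold at the two highest targets. At a ratio of 4.00, Day 15 exposure would be 1.33 or 1.78 times that of the target dose, for one infusion.

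This needs all of the following: dose level 5 or 6 cleared before the first Module 2 enrolment, the guidance ramp-up kept, a true ratio above 3.00 (at 3600 mg) or 2.25 (at 5400 mg), and exposure proportional to dose. Severity is minor to moderate. The SAP records that the sponsor terminated the study on 28 July 2023 with Module 2 ongoing when recruitment stopped, so the correction now serves the design record and any reuse of this design.

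**What to change.** State in 12.1.5 and Table 22 that in Module 2 Cycle 1 the Day 15 dose equals the Day 1 dose and is no more than about one quarter of the target dose.

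- **Preferred route.** Use a cleared target whose Module 1 ramp-up already starts at about a quarter: 2400 mg or below, or dose level 6 with the 1400/2800/5400 mg ramp-up (25.9%), which should be added to Table 22. The Figure 4 footnote would need to allow a target below the highest cleared dose. Section 12.1.5 already lets patients move to a higher tolerated target from Cycle 2.
- **Otherwise.** Use 900/1800/3600 or 1350/2700/5400 mg, only if the SRC accepts the 2-fold last step. This also needs a change to the 12.4.1 sentence tying the ramp-up to Module 1, and dose-reduction steps in Table 4 for 900, 1350, 1800 and 2700 mg.

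Separately, align the leftover one-quarter wording in SAP 11.1 with the rule adopted.

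**Cost.** A protocol dosing amendment and one editorial SAP change, with no added patients or procedures. The preferred route may mean a lower target dose in Cycle 1. The other route raises the Day 4 to Day 8 step from 1.5-fold to 2-fold (from 1200 to 1800 mg at the 3600 mg target, and from 1800 to 2700 mg at 5400 mg). That matters because the ramp-up exists to limit tumour lysis syndrome, and these two schedules are not among the ramp-ups the protocol lists for Module 1.

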2.1.2 Rationale for AZD0466 in treatment of haematological malignancies

AZD0466 is a drug-dendrimer conjugate that consists of the active moiety, the dual Bcl-2/Bcl-xL-specific inhibitor AZD4320, covalently conjugated to a pegylated poly-L-lysine type dendrimer, which gradually releases the active moiety by hydrolysis. AZD0466 was developed to mitigate the nonclinical toxicity findings observed with AZD4320.

Administration of AZD0466 results in lower peak plasma levels of AZD4320 than can be readily achieved by direct infusion of AZD4320 at similar exposure concentrations. Thus, AZD0466 exhibits potent Bcl-2/Bcl-xL-selective inhibition and has PK properties that minimise the potential for C_{max} -dependent Bcl-xL-mediated AEs.

In vitro, AZD0466 induces apoptotic cell death in a variety of tumour cell lines, with particularly broad activity in cell lines derived from haematological malignancies. It also demonstrates significant dose-dependent in vivo anti-tumour activity as a single agent across a range of human tumour xenograft and patient-derived models, including acute lymphoblastic leukaemia (ALL), acute myeloid leukaemia (AML), DLBCL, and small cell lung carcinoma. Enhanced nonclinical activity has also been observed for AZD0466 in combination with many standard-of-care anticancer therapies.

In nonclinical studies, anticipated on-target effects include rapid onset, transient abnormalities of hepatic transaminases, and thrombocytopenia. Based on nonclinical data, reduced QRS amplitude may also be observed at clinically predicted dose ranges. A detailed description of the chemistry, pharmacology, and nonclinical efficacy and safety of AZD0466 is provided in the Investigator's Brochure (IB).

AZD0466 has been administered to 9 patients with advanced solid malignancies at doses declared tolerable in the first-time-in-human study (D8240C00003). No dose-limiting toxicities (DLTs) have been recorded (data on file, AstraZeneca).

A detailed description of the chemistry, pharmacology, and nonclinical efficacy and safety of AZD0466 is provided in the IB.

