Plasma concentrations of AZD4320 will be summarised by nominal sample time. Plasma concentrations and derived PK parameters will be summarised by dose level and cohort. Plasma concentrations at each timepoint will be summarised according to dose and cohort by

the following summary statistics:

- The geometric mean (g_{mean} , calculated as $\exp[\mu]$, where μ is the mean of the data on a logarithmic scale)
- Coefficient of variation (CV, calculated as $100 \sqrt{[\exp(s^2)-1]}$, where s is the standard deviation of the data on a log scale)
- $G_{\text{mean}} \pm$ standard deviation (calculated as $\exp[\mu \pm s]$)
- Arithmetic mean calculated using untransformed data
- Standard Deviation calculated using untransformed data
- Minimum
- Maximum
- Number of observations

The following summary statistics will be presented for the estimated PK parameters, as appropriate:

- G_{mean} , calculated as $\exp[\mu]$, where μ is the mean of the data on a logarithmic scale)
- CV, calculated as $100 \sqrt{[\exp(s^2)-1]}$, where s is the standard deviation of the data on a log scale)
- Arithmetic mean calculated using untransformed data
- Standard deviation calculated using untransformed data
- Minimum
- Maximum
- Number of observations

The pharmacokinetic data for AZD4320 will also be displayed graphically. Displays will include AZD4320 (total and released) plasma concentration subject profiles (on the linear and log scale) versus time and G_{mean} concentration (\pm standard deviation) versus time, stratified by dose.

Statistical Analysis of Pharmacokinetic Data

For the statistical analyses, only patients who provide eligible PK data for both AZD0466 (Period 1) and AZD0466 + Voriconazole (Period 3) interventions will be included for statistical comparison. A comparison of the AZD0466 PK parameters C_{max} and AUC will be performed for AZD0466 + Voriconazole versus AZD0466 interventions.

Where data allow, the statistical analysis will be performed via a linear mixed effect model using the natural logarithm of AZD4320 C_{max} and AUC as the response variables with

intervention as a fixed effect, and patient as a random effect. Transformed back from the logarithmic scale, geometric means together with CIs (2-sided 95%) for C_{max} and AUC will be estimated and presented. Also, ratios of geometric means together with CIs (2-sided 90%) will be estimated and presented.

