4.13.4 Treatment of Outliers in Pharmacokinetic Analysis

If a value is considered to be anomalous due to being inconsistent with the expected PK profile, it may be appropriate to exclude this point from the PK analysis. However, the exclusion of data must have strong justification and will be documented in CSR.

Quantifiable pre-dose concentration values in the first dosing of cycle 1 (i.e., the first ramp-up dose) will be considered anomalous and set to missing for the PK analysis.

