11.1 Overall Study Design

Module 2, a Phase I DDI study of AZD0466 and the azole antifungal agent voriconazole, will be conducted in patients with AML or ALL to determine the effect of voriconazole on the PK of AZD0466. This module will be conducted in selected sites in parallel with Module 1. During periods of parallel enrolment, patient entry into Module 1 will be prioritised at sites conducting both Module 1 and Module 2 of this protocol.

The schedule in Cycle 1 involves dose ramp-up in from a starting dose of AZD0466 on Day 1 (one quarter of the target dose), with subsequent titration to the intermediate dose on Day 4 (one half of the target dose), and to the target dose on Day 8. Patients will receive a loading dosage of oral voriconazole followed by maintenance dosing in Cycle 1, as specified in the prescribing information for voriconazole (Voriconazole Prescribing Information). The dose of AZD0466 administered in combination with voriconazole will be one quarter of the target dose, to mitigate against a potential increase in exposure to the active moiety AZD4320 if a DDI exists between AZD0466 and voriconazole.

A visual representation of the DDI component of Module 2 (Cycle 1) is shown in [Figure 2](#).

Figure 2 Schema for Cycle 1 of Module 2

* The target dose (TD) of AZD0466 is the highest dose level determined as tolerated by the SRC in Part A of Module 1 at the point of first patient enrolment in Module 2.

**After reaching AZD0466 TD at D8 there will be a dose reduction on D15 to the D1 equivalent dose, with a return to full TD at the next AZD0466 administration day.

*** Voriconazole administration will be discontinued on Day 19 after collection of the last PK blood sample.

BID, twice a day; D, Day; IV, intravenous; PK, pharmacokinetic; PO, by mouth; RU1: first ramp-up dose; RU2: second ramp-up dose; SRC, Safety Review Committee; TD, target dose.

A minimum of 10 and up to 14 patients overall will be enrolled at selected sites to investigate the potential DDI between AZD0466 and voriconazole.

The DDI part of Module 2 (Cycle 1) will be performed in 3 periods over 21 days, as follows:

Period 1 (Days 1-10): AZD0466 infusion on Days 1, 4, and 8

Period 2 (Days 11-14): Voriconazole administration bid

Period 3 (Days 15-21): AZD0466 infusion (at the Day 1 equivalent dose) on Day 15 in combination with voriconazole bid on Days 15-19.

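### Module 2's interaction ratio compares a drug-naive Day 1 profile with a Day 15 profile taken 7 days after a larger dose, and no carry-over adjustment is specified

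*Protocol*

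**What the plan says.** Protocol 12.1.5 sets Period 1 as "AZD0466 infusion on Days 1, 4, and 8" and continues: "After reaching the target dose at Day 8, there will be a dose reduction at Day 15 to the Day 1 equivalent dose". Voriconazole begins 72 h after the Day 8 infusion: "Patients will receive voriconazole 400 mg twice daily (BID) on Day 11" (protocol 12.4.1).

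The interaction is assessed within patient. Under protocol 12.7.8.1, "only patients who provide eligible PK data for both AZD0466 (Period 1) and AZD0466 + Voriconazole (Period 3) interventions will be included". The model is on log Cmax and log AUC and contains only intervention and patient. SAP 10.1 names AUC0-72, AUClast and Cmax, for total and released AZD4320, and SAP 11.2.2 takes them from the Day 1 and Day 15 profiles.

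On pre-dose values the SAP covers only the first dose of Cycle 1. Section 4.13.3 imputes a missing one. Section 4.13.4 deals with a measurable one: "Quantifiable pre-dose concentration values in the first dosing of cycle 1 (i.e., the first ramp-up dose) will be considered anomalous", and sets it to missing. A pre-infusion sample is scheduled on Day 15 and Ctrough is derived, but neither document uses it to adjust the Day 15 AUC or Cmax. SAP 12.11 only points back to 4.13.

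**The concern.** Equal doses on Days 1 and 15 stop a dose change from being mistaken for an interaction. They do not make the starting conditions equal. Day 1 begins with no AZD4320 in the body. Day 15 begins with whatever is left from three infusions, the largest given 168 h before. The product is a conjugate "which gradually releases the active moiety by hydrolysis" (protocol 2.1.2), so a residual at 7 days is plausible. From Day 11 voriconazole may also slow clearance of the released part.

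With no term or rule for this, any residual is credited to voriconazole. The error runs in one direction, and more patients would not remove it. For total AZD4320, which includes conjugated drug, a ratio above 1 could appear without any CYP3A4 effect. The result matters because it "will inform the continuation or removal of restrictions on use of azole antifungal agents" (protocol 12.1.3).

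**Working it through.** **The plan's own figure (protocol 12.7.2).** Inputs: intrapatient CV 30%, 10 evaluable patients, 90% CI limit ratio of 2.0 with probability above 80%, illustrated as 2.83 to 5.66 around 4.00.
- s_w = sqrt(ln(1 + 0.30²)) = 0.2936.
- 4/√2 = 2.83 and 4 × √2 = 5.66, a factor of 1.41 each side.
- At n = 10 the probability of a limit ratio of 2.0 or less is 97.2%, so the statement reproduces. The expected CI is narrower: exp(t(0.95, 9) × 0.2936 × sqrt(2/10)) = 1.27 each side.

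**Dose ratios (protocol Table 22).** Day 8 over Day 1: 300/75, 600/150, 1200/300 and 2400/600 = 4; 3600/1200 = 3; 5400/2400 = 2.25. Day 4 over Day 1 is 2, and 1.5 in the last row.

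**Carry-over with no true interaction.** The half-life h is assumed, because the documents give none. With linear, mono-exponential decline, the residual at the Day 15 infusion, as a fraction of one Day 1 dose, is

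R = r·2^(−168/h) + m·2^(−264/h) + 2^(−336/h),

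where r and m are the Day 8 and Day 4 dose ratios. The apparent AUC0-72 ratio is 1 + R. Example at h = 48 h, 4:1: 4 × 0.0884 + 2 × 0.0221 + 0.0078 = 0.406.

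| Half-life | 4:1 | 3:1 | 2.25:1 |
|---|---|---|---|
| 24 h | 1.03 | 1.02 | 1.02 |
| 36 h | 1.17 | 1.13 | 1.10 |
| 48 h | 1.41 | 1.32 | 1.24 |
| 72 h | 1.99 | 1.79 | 1.60 |

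At 12 h the ratio is 1.00 in every column. At 4:1 the inflation reaches 5% at 26 h, 10% at 31 h and the expected CI factor of 1.27 at 42 h. At 2.25:1 these points are 30, 36 and 50 h.

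**If voriconazole slows elimination from Day 11.** With k = ln 2/h and clearance divided by f from hour 240, R = [r·e^(−72k) + m·e^(−168k) + e^(−240k)]·e^(−96k/f). At 4:1 and f = 2, R is 0.13, 0.43, 0.81 and 1.57 at half-lives of 24, 36, 48 and 72 h. At f = 4, the size of effect used in 12.7.2, R is 0.26, 0.69 and 1.15 at 24, 36 and 48 h. This inflation comes on top of any real effect. It applies to released AZD4320 only, since release from the dendrimer is by hydrolysis.

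**AUClast.** It can run to 96 h on Day 15 but only 72 h on Day 1. With no interaction and no residual, (1 − 2^(−96/h))/(1 − 2^(−72/h)) = 1.07 at 24 h and 1.16 at 48 h.

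**Can the residual be subtracted?** SAP 11.2.2 wants the terminal slope estimated over at least two half-lives where possible. The Day 15 profile ends at 96 h, so a 48 h half-life would use all of it and a 72 h half-life would need 144 h. Where the slope is not usable, subtracting a constant Cpre over 72 h gives a lower limit for AUC0-72. In the 4:1, no-interaction model, that subtraction, in units of the Day 1 AUC0-72, is R × 72k/(1 − e^(−72k)):
- 48 h: 0.406 × 1.040/0.646 = 0.65, giving a range of 0.75 to 1.41.
- 72 h: 0.991 × 0.693/0.5 = 1.37, giving 0.62 to 1.99.

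Both ranges contain the true value of 1.00. They are wide.

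**The case against.** A reader might infer that the carry-over is undetectable. The documents do not support that. Module 1 (protocol 11.6.3.1.2) samples before the Cycle 2 Day 1 infusion, 7 days after the Day 29 target dose, and follows Day 8 to 72 h. In Module 2 the Day 15 Ctrough is derived and would be summarised.

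A reader might also infer that Module 2 has no PK sample between the Day 4 end of infusion and Day 15. The sampling table in 12.6.3.1.1 lists none, but Table 27 marks the Day 8 ECGs as belonging to a PK visit and the protocol's AUCcml runs through Day 8. The documents conflict here, so absence is not established.

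A third inference is that the ratio is known to be badly inflated, or that azoles would wrongly stay prohibited. No half-life is given, the mono-exponential model is at the upper end, and the protocol sets no ratio at which the restriction would be lifted. With an expected ratio near 4, a modest bias might not alter the decision.

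Two further points stand. The cited AstraZeneca PK standards are not available here and might contain a pre-dose rule. SAP version 2.0, written after termination, no longer describes the geometric mean ratio or mixed model, so an adjustment there has nothing to attach to until that comparison is restored.

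None of this removes the core point. Deriving Ctrough shows a residual but does not take it out of the ratio, and the visible text contains no step that does.

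**Conclusion.** The concern holds as a one-directional bias of unknown size in the module's only interaction estimate. The schedule and the missing adjustment are established from the protocol and SAP text. The size depends on the assumed half-life: about 3% or less up to 24 h with no interaction, 17% at 36 h, 41% at 48 h and a doubling at 72 h, all at 4:1 with mono-exponential, linear kinetics. It is smaller for the two highest rows of Table 22 and for a multi-phase profile, and larger for released AZD4320 if voriconazole slows its clearance from Day 11. No realistic figure for Cmax can be given.

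This is more than a missing detail, because following the stated analysis exactly can give a wrong ratio. It should be corrected.

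**What to change.** - Carry the protocol's interaction comparison into SAP 11.2.2 and 12.11. There and in protocol 12.7.8.1, pre-specify carry-over-adjusted Day 15 AUC0-72 and Cmax, for total and released AZD4320, beside the uncorrected values.
- Where lambda_z meets the SAP's two-half-life span, subtract Cpre × exp(−lambda_z × t) from the Day 15 profile, with Cpre the Day 15 pre-infusion concentration.
- Where it does not, report AUC0-72 as a range from the value with a constant Cpre subtracted over 72 h up to the uncorrected value. This assumes that the residual does not rise after Day 15.
- List Day 15 Cpre as a percentage of Day 15 Cmax for each patient.
- Base the interaction conclusion on AUC0-72 rather than AUClast.
- Reconcile the sampling table with Table 27 on Day 8. Also reconcile SAP 11.1, which describes "a starting dose of AZD0466 on Day 1 (one quarter of the target dose", with Table 22, where that fraction holds only in the first four rows.

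The cost is wording and a small extra non-compartmental step, with no new samples or patients. The adjustment is approximate, and for patients without a reliable lambda_z it gives a range, possibly a wide one, rather than a point value. If pre-dose levels prove trivial, the listing will show it.
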